### **Sources of Materials.**

The research material that will be collected from human subjects will be of two forms. First, in the case of participating midwives, tests of knowledge and competence with the technology and mHealth interface will be administered by project staff. Performance data on these tests will be tabulated in an electronic spreadsheet, where each midwife will be identified by a unique identification number. A separate master sheet linking these unique numbers to each participating midwife will be maintained, accessible only by the principal investigators. At the end of the data entry and data cleaning phases, this master sheet will be destroyed. All data will be stored on a secure, HIPAA-compliant server.

Second, demographic and health outcomes data will be entered on each participating pregnant woman and resulting neonate into both paper forms and the mHealth interface. Paper forms will be collected by local field staff, checked against the EMR for accuracy, and then immediately destroyed. Each patient entered into the EMR in this way will have a unique electronic medical record number, and the project's principal investigators will maintain a list of these medical record numbers on a secure, HIPAA compliant server. Only the PI's will have access to this list. At the end of the project, this list will be used to extract the relevant outcomes data from the EMR, at which point the data will be deidentified and the master list of medical record numbers will be destroyed.

No identifiable data will be removed from the Wuqu' Kawoq servers, and will be de-identified before being downloaded to Emory University servers in the United States.

### **Potential Risks to Participants**

The potential risks to participants from this project are minimal. For participating midwives, there is the potential risk that early randomization to the technology will create resentment among midwives who receive late randomization to the technology. To minimize this risk, all participants will receive an extensive orientation to the project design to the need to collect baseline data from half of the participants. Participants will also be reassured that all will receive equal training and access by the end of the project.

The risks to participating pregnant women and neonates are also minimal. The technologies that will be used in the project are well validated and noninvasive (Doppler ultrasound, pulse oximetry, and automated blood pressure) and routinely used worldwide in standard of care prenatal health. Therefore, no new or invasive technologies that might pose a risk to pregnancy outcomes will be employed. Furthermore, the algorithms that the mHealth interface will employ are highly conservative and designed to promote referral to physicians and to higher levels of medical care. In other words, the algorithms are designed never to "downgrade" an individual midwife's level of clinical concern and would the decision support component would never suggest against medical referral. This means

that the risk that the project would decrease health care access or falsely reassure midwives against a referral is minimal.

There is also risk of psychological stress or stigma to participating pregnant women who, for cultural or family reasons may choose to conceal the fact of their pregnancy to all but the consulting midwife. Participating in this project may contribute to inadvertent disclosure of pregnancy status to community or family members. In order to minimize this risk, project staff will limit direct interactions with enrolled pregnant women during the course of the project after obtaining consent. In other words, confidentiality and intimacy in the patient-midwife relationship will be maintained to the greatest degree possible. Project staff will interact only with the midwife and will collect relevant data only from the midwife, off-site and not within the community.

One final risk is that incorrect use of the technology may lead to a reading of an absent, excessively low or excessively high heart rate, and the relating of this information to the patient would lead to unnecessary emotional stress. Although our device is specifically designed to avoid such scenarios we will provide specific training to the midwives at the WK main site. We will follow standard training patterns, familiar to the midwives, for assembling midwives in small groups in a training room, which simulates the rural environment. The research team will provide training to the consented midwives using volunteer pregnant women. Training will be given on:

- How to interact with the consenter to allow non-coercive consent prior to any use of the study equipment or discussion of its utility.
- How to explain what they are doing during the data collection.
- How to answer questions about data use (after consent).
- How to use the device to obtain a good signal, and recognize when the signal is poor.
- How to ensure data is saved and later uploaded.
- How to label the data back to the patient in a de-identified manner if required.
- How to react to scenarios that may lead to stress on the patient such as:
  - Finding no heart beat
  - Heartbeat is too fast/slow
  - Device does not work
  - Device feels 'uncomfortable'

(In the first two cases the midwife would not reveal a problem initially to the patient, but will be trained to talk to a back-up Wuqu' Kawoq physician directly prior to disclosure).

In order to participate in the study, the midwife will have to be able to use all parts of the device correctly, and react correctly in the above scenarios. The study coordinator will assess each of the midwives for passing this test and certify that they are ready to participate. The study coordinator will also visit midwives at random in the study environment and identify deviations from the protocol requiring retaining and recertification.

## **Adequacy of Protection Against Risks**

### **Recruitment and Informed Consent**

Written or verbal informed consent will be obtained from all participating midwives and also from all pregnant patients of each participating midwife. There are two distinct settings and population for consenting study participants. The first group of participants is the midwives, who will be recruited and consented by the study coordinator at Wuqu' Kawoq. Midwives in Wuqu' Kawoq's catchment area will be contact by phone by the study coordinator to assess interest in the project. If a midwife expresses interest in participating they will be invited to a preliminary training session. During this training session, project staff (and in particular the study coordinator) will describe the full details of the study to potential midwife participants, including the nature of the subject's involvement in the study, the possible risks and benefits of participation, and the individual capacity to withdraw from the study at any time without consequence. The midwives will have the opportunity to ask questions about the study, after which consent to proceed will be obtained. The study coordinator will receive training in human subjects protection (e.g., CITI or the NIH module) prior to interacting with and obtaining consent with midwives.

The second group of participants that requires consenting is the pregnant mothers. All pregnant patients of each recruited midwife will be eligible for participation. Participating midwives will be encouraged to mention the study to all of their patients and to relay any potential interest in participating to the study coordinator. When a midwife identifies a pregnant subject for potentially participation, a single study staff member (a trained nurse working under the supervision of the study coordinator) will discretely visit the patient (and the biological father, if appropriate), at a location of their choosing (most likely to be the domicile of the pregnant patient) and again describe the details of the study, the risks and benefits, and the capacity to withdraw at any time without consequence, at which point verbal consent will be obtained for collection of data both during the pregnancy and in the neonatal period.

Both midwives and patients will all be bilingual speakers of Spanish and Kaqchikel Maya. Spanish is the language that they use for technical conversations, such as medical conversation. Kaqchikel is an oral, non-written language that is used in more colloquial settings. Therefore, consent (and consent documents) will be obtained in Spanish, although research staff will be able to speak both languages. We anticipate that some informal conversation and question answering will occur in Kaqchikel, after the formal consent has been read, as this is typical of medical consultations and interactions in the region: technical conversation in Spanish followed by informal clarification in Kaqchikel. In our previous experiences, we have been able to obtained written informed consent successfully, as long as attention is paid to providing clear orientation and allowing time for informal clarification and question answering. Wuqu' Kawoq's field staff all are native Spanish and Kaqchikel Maya speakers.

## **Protection Against Risk**

Confidentiality To protect confidentiality, the following steps will be taken: All paper research forms will be kept in locked file cabinets and will be available only to research staff directly involved in this project. Immediately after checking paper forms against the mHealth/EMR interface, they will be destroyed. The EMR will be maintained on a secure, HIPAA-compliant cloud server, and only the principal investigators will have access to the EMR directly. Master lists of participating midwives and patients will be keyed to unique identifying numbers, and only the project principal investigators will have access to these

keys, which will also be maintained separately on a secure, HIPAA-compliant cloud server. One data extraction and cleaning has been completed, these master lists will be destroyed, and data in the analysis phase will be completely deidentified. Laptop computers or tablets used for data entry will be routinely backed-up and will be password-protected and encrypted.

**Additional Protections for Pregnant Women, Fetuses and Neonates.** This research involves the collection of demographic and health outcomes data on pregnant women and neonates. Importantly, the interventional component of the study involves an mHealth/EMR integration step and does not introduce novel or experimental technologies. All technologies that will be used in the mHealth arm are standard-of-care technologies (Doppler, blood pressure monitoring, pulse oximetry). Half of the enrolled participants will initially not receive any intervention. However, they will receive the current standard of care by lay midwives, with no interference in this usual process. Furthermore, for pregnant women and neonates who access the technology (either in the early access or later access arms), the expected result of the technology will be earlier and more timely referral to a higher level of medical care. At no point will the technology discourage accessing a higher level of care. Since the project holds out the potential for direct benefit to the pregnant woman and/or her fetus, consent will be obtained directly from the pregnant women to participate as outlined in 45cfr46 subpart B. The proposal does not include any inducements to early termination of a pregnancy, and it does not explicitly involve research on neonates of uncertain or non-viability, although in accordance with the proposal's plan to increase early access to medical care for all neonates, rates of neonatal mortality will be tracked.

**Additional Protections for Children.** This study involves collection of neonatal mortality rates and rates of early evaluation of neonates by a postnatal health care delivery team. As such, no direct interventions on children will be performed, and the study involves minimal risk to children. As outlined above, consent will be obtained from both biological parents at the time of enrollment of the pregnant patient in the study to permit collection of this data.

The study will not enroll pregnant patients prior to the legal age of informed consent in Guatemala (18 years).

**Adverse Events.** In the event that midwives either in the early technology access or later access arms detect the need for a referral to a higher level of medical care or an adverse event, they will be instructed to proceed with arranging the referral through the usual local mechanisms. However, the local site partner, Wuqu' Kawoq, will also designate a medical officer to assist with the project, and this physician will be available to all midwives throughout the duration of the project to provide further logistical and decision support for arranging referrals and management of adverse events.

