Of the 50 recruited midwives, 25 will be randomly assigned to receive access to the mHealth technology immediately, whereas the remaining 25 will receive the technology after 6 months. Randomization of the midwives will be performed by entering their IDs into a list and running a simple program to generate an equal number of 1's and zeros, uniquely assigned to each midwife ID. For the second half of the 12 month implementation phase, all 50 midwives will have access to the technology. This randomized "stepped wedge" design is critical to the evaluation of the project, since baseline data (for example, on referral rates to local hospitals) is not readily available. Therefore, randomizing 50% of the enrolled midwives to a delayed intervention phase will allow us to collect high quality internal baseline data that can be used to make comparisons to the early intervention arm (e.g., to compare rates of referral). At the 6 month time-point, all midwives who did not initially receive the technology will do so, which will allow all participating midwives to benefit from the training and technology by the end of the project.

In the proposed work site, midwives attend on average 10-20 births per year. This means that, over 12 months of implementation, we will have the opportunity to collect process and outcomes data on a minimum of 500 pregnant women and neonates. We will restrict enrollment of pregnant women to those who are older than 18 years of age. This is the legal age of consent in Guatemala, and this is a necessary arrangement to ensure that only consenting adults are participating in the project, as opposed to minors who are pregnant. The average age of first pregnancy in the region is 22 years of age, so the number of pregnant women who are excluded from the project due to being legal minors will be minimal. Selection of patients will be on an ad hoc basis, based on the willingness and availability of patients.

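### Does the project physician's referral support make the delayed arm something other than the usual-care comparator the protocol describes?

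*Protocol*

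**What the plan says.** Under Human Subjects Involvement, Characteristics, and Design, the protocol randomises 50 midwives, 25 to the technology at once and 25 after 6 months. It gives as the reason that "baseline data (for example, on referral rates to local hospitals) is not readily available". The delayed half is to supply internal data against which the early half can be compared, with referral as the example.

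Under Protection Against Risk, the part on additional protections for pregnant women, fetuses and neonates says that "the interventional component of the study involves an mHealth/EMR integration step". It continues: "Half of the enrolled participants will initially not receive any intervention". Of that half it then says that "they will receive the current standard of care by lay midwives, with no interference in this usual process".

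The Adverse Events paragraph covers the case in which "midwives either in the early technology access or later access arms detect the need for a referral", so it applies to both arms. First, "they will be instructed to proceed with arranging the referral through the usual local mechanisms". Then it adds that the local partner will name a medical officer for the project, and that "this physician will be available to all midwives throughout the duration of the project to provide further logistical and decision support for arranging referrals".

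A separate physician contact appears under Potential Risks to Participants. A midwife who finds no heartbeat, or an abnormal one, with the device "will be trained to talk to a back-up Wuqu' Kawoq physician directly prior to disclosure". The protocol does not say whether this is the same physician.

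**The concern.** Side by side, the two statements under Protection Against Risk seem to describe different comparators. One gives usual lay-midwife care left alone. The other gives usual care plus a project physician who can be called on for decisions and logistics when a referral is arranged. The protocol's wording presents the physician as an addition to the usual route, and nowhere calls this support usual care.

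The support bears on referral, the one outcome that the design section names for the comparison between arms. If help from the physician changes how often midwives refer, the delayed arm's rate is not the rate that would be seen without the project. The technology's effect would also be measured on top of that help. A reader who saw only the no-interference sentence could then take the delayed-phase rate as the missing local baseline, or carry the result over to places without such back-up. The section on the importance of the knowledge to be gained does look towards other rural populations.

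**Working it through.** The protocol gives no referral rate, effect size or power figure on this point, so there is no stated number to reproduce. The check is a reading of the passages and a short piece of reasoning about what the comparison estimates.

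**1. Who has what, in months 1 to 6** (the only period with a comparison between technology and no technology)

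| | Early arm | Delayed arm |
|---|---|---|
| Midwives | 25 | 25 |
| Midwife-months | 25 × 6 = 150 | 25 × 6 = 150 |
| Technology | yes | no |
| Physician for referral support (Adverse Events) | available in 150 of 150 | available in 150 of 150 |
| Physician contact after a device finding (Potential Risks) | possible | not possible without the device |

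These counts show availability, not use. They establish that the offer is balanced and say nothing about the size of any effect.

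**2. What the comparison estimates**

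Write R(t, p) for the expected referral rate, with t = 1 if the midwife has the technology and p = 1 if the project physician is available.

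- Early arm: R(1, 1).
- Delayed arm: R(0, 1).
- Randomised contrast: R(1, 1) − R(0, 1).

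Because p = 1 on both sides, the contrast is the effect of the technology where back-up is available. No bias enters through p. If the two effects add, R(t, p) = a + b·t + c·p, the contrast is (a + b + c) − (a + c) = b and c drops out whatever its size. If they interact, the contrast is still a valid effect for the setting with back-up, though it may differ from R(1, 0) − R(0, 0).

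The quantity not observed is R(0, 0). The gap R(0, 1) − R(0, 0) has neither size nor sign in the document. It is zero if midwives could already reach such a physician, which the protocol does not settle.

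**3. Does the plan need R(0, 0)?**

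The design section wants internal data for comparison with the early arm. That requires R(0, 1), which the delayed arm supplies. The plan does not promise an estimate of referral without physician back-up.

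**4. Is there a contradiction in the text?**

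- The statement that half receive no intervention is consistent, because the same paragraph defines the interventional component as the mHealth/EMR step.
- The no-interference phrase stands in a passage on protecting women and neonates and follows directly on the admission that half get no intervention. There it reads as an assurance that these women lose nothing.
- The Adverse Events paragraph keeps the usual referral route as the instruction. The physician is available, not required. Optional help does not impede usual care.
- That paragraph names both arms, all midwives and the whole project, so the protocol as a whole does say what the delayed arm receives.

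**5. The contact after a device finding**

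This differs between arms, but it arises only through use of the device. It is part of the technology package being tested, not an imbalance in background care.

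**The case for a change.** The strongest case for a change is that the no-interference phrase does more than reassure: it completes a sentence about what the comparator receives, and an added source of decision support for referral is then left out. The protocol also speaks of decision support for the technology's own algorithms, so the comparator has access to help of a related kind. With no external baseline, the delayed-phase rate is likely to be cited as one. A qualifying phrase would cost almost nothing, and a log of physician contacts would show how much the back-up was used.

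Part of this stands. The delayed-phase rate should be understood as observed with a project physician available, and a cross-reference between the two paragraphs would have been tidier. But the possible misreading needs one paragraph to be read without its neighbour, and the phrase would alter no allocation, outcome or analysis. The log would be new data collection that describes uptake only; it could not recover a rate without back-up. It would also ask the physician to record midwife identifiers whose keys the protocol restricts to the principal investigators. Its gain does not justify making it a requirement.

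**Conclusion.** The concern does not call for a change. The physician support is disclosed, offered equally to both arms and optional. Followed as written, the plan gives a randomised comparison with no bias from this source, and the delayed arm serves the purpose that the design section sets for it.

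The residue is editorial: neighbouring paragraphs lack a cross-reference. Authors will ordinarily describe the comparator as lay-midwife care with a project physician available, and read the delayed-phase referral rate in that light.

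This rests on two assumptions: that the physician is in fact equally available to both arms, as the Adverse Events paragraph states, and that the delayed-phase rate is used as an internal comparator and not as an estimate of referral without the project. The effect of the back-up on referral cannot be sized from the document, and none is assumed. Nothing here questions the support itself.

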### **Potential Benefits to Study Participants**

Participants are likely to benefit directly from this project. Midwives will benefit by gaining access to additional medical knowledge and technology. Pregnant women and neonates will benefit by earlier detection of the need for medical referral and improved care coordination. The risk of the project are minimal, and the potential benefits of the project, which include the demonstration that mHealth technology can be used to enhance the care provided by lay midwives in a developing country setting where perinatal outcomes and care coordination are generally poor outweigh these risks.

### **Importance of the Knowledge to Be Gained**

The information gained through this project will contribute important, practical insights into the implementation of a mHealth solution to low rates of medical referral and care coordination for pregnant women and neonates. These are perennial public health problems in rural Guatemala which have until now proven to be largely intractable. In addition to suggesting new avenues for enhancing care in rural Guatemala, the results will also be applicable to other rural populations in other developing countries which experience similar breaks in the primary care referral chain and the continuum of care.

